8.3 Definitions, Derived Variables, and Data Sets

8.3.1 Baseline

Baseline value is defined as the predose value on Cycle 1 Day 1 or the last observation before start of drug if the predose value on Cycle 1 Day 1 is missing.

8.3.2 Date/Time Definitions

The following factors will be used to convert days to months or years:

1 month = 30.4375 days

- Time from first diagnosis to first dose (months) is:
(Date of first dose – Date of first diagnosis) / 30.4375
- Time from first metastatic diagnosis to first dose (months) is:
(Date of first dose – Date of first metastatic diagnosis) / 30.4375
- Time from last medication to first dose (months) is:
(Date of first dose – End date of last medication) / 30.4375
- Time from last procedure to first dose (months) is:
(Date of first dose – Start date of the last anti-cancer procedure) / 30.4375
- Time from last radiotherapy to first dose (months) is:
(Date of first dose – End date of the last radiotherapy) / 30.4375
- Time from last radioiodine therapy to first dose (months) is:
(Date of first dose – End date of the last radioiodine therapy) / 30.4375

8.3.3 Radioiodine Therapy Conversions

The SI unit for radioiodine therapy is GBq (1 gigabecquerel = 10^9 Bq). Data was also collected with the unit mCi (millicuries). The conversion is 1 mCi = 0.037 GBq.

8.3.4 Creatinine Clearance

The pediatric Schwartz equation for creatinine clearance is:

- $\text{GFR} (\text{mL/min}/1.73 \text{ m}^2) = (0.41 \times \text{Height}) / \text{Scr}$, where Scr is serum/plasma creatinine in mg/dL

8.3.5 Last Known Alive Date

The last date the subject was known to be alive should be derived from survival follow-up date or the latest date among last treatment date, last radiologic follow-up date, last laboratory assessment date, last AE date, last concomitant medication date, or last vital sign measurement date.

8.4 Pharmacokinetics/Pharmacodynamics Data Handling

8.4.1 Lower Limit of Quantification of Lenvatinib Plasma Concentration

The lower limit of quantification (LLOQ) of lenvatinib plasma concentration is 0.25 ng/mL.

8.4.2 BLQ Handling for Developing Concentration-Time Profiles

When calculating the mean or median value for the concentration at a given time point, the BLQ values will be assigned as zero. If the proportion of values reported as BLQ is more than 50%, no summary statistics should be represented at that time point, and the value will be treated as missing in mean or median concentration profiles.

9 PROGRAMMING SPECIFICATIONS

The rules for programming derivations and dataset specifications are provided in separate documents.

10 STATISTICAL SOFTWARE

Statistical programming and analyses will be performed using SAS® (SAS Institute, Inc., Cary, NC, USA), version 9 or higher, and/or other validated statistical software as required.

11 MOCK TABLES, LISTINGS, AND GRAPHS

The TLG shells will be provided in a separate document, which will show the content and format of all tables, listings, and graphs in detail.

13 APPENDICES

13.1 Dose-Limiting Toxicities

Dose-limiting toxicity (DLT): A DLT in subjects treated with lenvatinib will be assessed according to Common Terminology Criteria for Adverse Events (CTCAE) v4.03 and is defined as any of the following toxicities related to lenvatinib or chemotherapy drugs (ifosfamide and/or etoposide) occurring during Cycle 1 (Day 1 to Day 28) for Cohort 1 and during Cycle 1 (Day 1 to Day 21) for Cohort 3A.

- Hematologic Toxicity
 - Grade 4 neutropenia for ≥ 7 days (≥ 10 days for Cohort 3A)
 - Grade ≥ 3 thrombocytopenia with bleeding, or lasting >7 days (≥ 10 days for Cohort 3A)
 - Grade ≥ 3 febrile neutropenia (lasting ≥ 7 days for Cohort 3A)
 - Next course of chemotherapy delayed for ≥ 7 days (Cohort 3A)
- Nonhematologic toxicity
 - Grade ≥ 3 nonhematological toxicity persisting more than 7 days despite optimal supportive care. Isolated laboratory abnormalities that resolve within a week, allergic reactions, and symptoms related to tumor progression will be excluded.
 - Grade 4 hypertension, confirmed systolic or diastolic blood pressure more than 25 mmHg above the 95th percentile for age, or an elevated diastolic blood pressure (ie, >95 th percentile for age) not controlled by a single antihypertensive medication within 14 days of use. An antihypertensive tablet or capsule that contains up to two antihypertensive ingredient medications will count as one antihypertensive medication.
 - Grade 3 proteinuria
 - Any recurrent Grade 2 nonhematological toxicity requiring ≥ 2 interruption and dose reductions
- Any dose interruption or reduction due to toxicity which results in administration of less than 75% of the planned dosage of lenvatinib.
- Any other Grade ≥ 3 toxicity (hematologic and nonhematologic) assessed as related to lenvatinib treatment, and which in the opinion of the principal investigator and Eisai medical monitor constitutes a dose-limiting toxicity

All DLTs must be reported to the Eisai medical monitor within 24 hours of their occurrence. Determination of a DLT will be made by the investigator and Eisai Medical Monitor in consultation with the PSC, as needed. Subjects who discontinue study drug for any reason other than DLT during Cycle 1 (Day 1 to Day 28) for Cohort 1 and Cycle 1 (Day 1 to Day 21) for Cohort 3A will be replaced.

13.2 Summary of Efficacy Analyses

Efficacy Variable	Analysis Set	Statistical Method	Tumor Assessments
PFS-4	Full Analysis Set, Per Protocol Analysis Set	Number (percent) of subjects who are alive, free of disease progression, and did not receive anticancer medication 4 months after the first dose, and its exact 80 and 95% CIs using method of Clopper and Pearson.	Investigator
		Cohort 2B: PFS-4 rate will be tested using a Null hypothesis that PFS-4 is $\leq 25\%$ tested against the alternative hypothesis of a PFS-4 $\geq 45\%$, using the 1-sample exact test of a single proportion, at the 1-sided 0.1 level.	
ORR	Full Analysis Set, Per Protocol Analysis Set	Cohort 3B: PFS-4 rate will be tested using a Null hypothesis that PFS-4 is $\leq 25\%$ tested against the alternative hypothesis of a PFS-4 $\geq 50\%$, using the 1-sample exact test of a single proportion, at the 1-sided 0.1 level.	Investigator
PFS	Full Analysis Set, Per Protocol Analysis Set	Number (percent) of subjects (with PR + CR) and its exact 95% CI using method of Clopper and Pearson.	Investigator
OS	Full Analysis Set	KM method: Median, Q1, and Q2 PFS will be presented, with 2-sided 95% CIs (Brookmeyer and Crowley). Cumulative probability of PFS at 4 and 12 months will be presented with 2-sided 80 and 95% CIs (Greenwood using the log-log). KM plot will also be provided.	Not Applicable

Efficacy Variable	Analysis Set	Statistical Method	Tumor Assessments	
		plot will also be provided.		
BOR	Full Analysis Set, Per Protocol Analysis Set	Number (percent) and 95% exact CIs will be provided for each BOR category	Investigator	
DOR	Full Analysis Set, Per Protocol Analysis Set	KM method: Median, Q1, and Q2 PFS will be presented, with 2-sided 95% CIs (Brookmeyer and Crowley).	Investigator	
TTP	Full Analysis Set, Per Protocol Analysis Set	Kaplan-Meier method: Median, Q1, and Q2 TTP will be presented with 2-sided 95% CIs (Brookmeyer and Crowley). Cumulative probability of TTP at 4 and 12 months will be presented with 2-sided 80 and 95% CIs (Greenwood using log-log). Kaplan-Meier plot will also be provided.	Investigator	

Efficacy Variable	Analysis Set	Statistical Method	Tumor Assessments
DCR	Full Analysis Set	Number (percent) of subjects (measurable disease with CR + PR + stable disease [SD] \geq 7 weeks, evaluable disease with CR + Non-CR/Non-PD \geq 7 weeks) and its exact 95% CI using method of Clopper and Pearson.	Investigator
CBR	Full Analysis Set	Number (percent) of subjects (measurable disease with CR+ PR + SD \geq 23 weeks, evaluable disease with CR + Non-CR/Non-PD \geq 23 weeks) and its exact 95% CI using method of Clopper and Pearson.	Investigator

13.3 Common Terminology Criteria For Adverse Events (CTCAE) For Hematology & Clinical Chemistry

Laboratory	Common Terminology Criteria for Adverse Events (CTCAE)			
	Grade 1	Grade 2	Grade 3	Grade 4
Parameter				
Hematology				
Hemoglobin	< LLN – 10 g/dL < LLN – 6.2 mmol/L	< 10 – 8 g/dL < 6.2 – 4.9 mmol/L	< 8 – 6.5 g/dL < 4.9 – 4 mmol/L	–
Platelet Count	< LLN – 75,000/mm ³ < LLN – 75 x 10 ⁹ /L	< 75,000 – 50,000/mm ³ < 75 – 50 x 10 ⁹ /L	< 50,000 – 25,000/mm ³ < 50 – 25 x 10 ⁹ /L	< 25,000/mm ³ < 25 x 10 ⁹ /L
Leukocytes (Total WBC)	< LLN – 3,000/mm ³ < LLN – 3 x 10 ⁹ /L	< 3,000 – 2,000/mm ³ < 3 – 2 x 10 ⁹ /L	< 2,000 – 1000/mm ³ < 2 – 1 x 10 ⁹ /L	< 1,000/mm ³ < 1 x 10 ⁹ /L
Lymphocytes (hypo)	< LLN – 800/mm ³ < LLN – 0.8 x 10 ⁹ /L	< 800 – 500/mm ³ < 0.8 – 0.5 x 10 ⁹ /L	< 500 – 200/mm ³ < 0.5 – 0.2 x 10 ⁹ /L	< 200/mm ³ < 0.2 x 10 ⁹ /L
Lymphocytes (hyper)	–	> 4,000 – 20,000/mm ³ > 4 – 20 x 10 ⁹ /L	> 20,000/mm ³ > 20 x 10 ⁹ /L	–
Neutrophils	< LLN – 1,500/mm ³ < LLN – 1.5 x 10 ⁹ /L	< 1,500 – 1,000/mm ³ < 1.5 – 1 x 10 ⁹ /L	< 1,000 – 500/mm ³ < 1 – 0.5 x 10 ⁹ /L	< 500/mm ³ < 0.5 x 10 ⁹ /L
Clinical Chemistry				
Albumin	< LLN – 3 g/dL < LLN – 30 g/L	< 3 – 2 g/dL < 30 – 20 g/L	< 2 g/dL < 20 g/L	
Alkaline Phosphatase	> 1 – ≤ 2.5 x ULN	> 2.5 – ≤ 5 x ULN	> 5 – ≤ 20 x ULN	> 20 x ULN
ALT	> 1 – ≤ 3 x ULN	> 3 – ≤ 5 x ULN	> 5 – ≤ 20 x ULN	> 20 x ULN
Amylase	> 1 – ≤ 1.5 x ULN	> 1.5 – ≤ 2 x ULN	> 2 – ≤ 5 x ULN	> 5 x ULN

Laboratory	Common Terminology Criteria for Adverse Events (CTCAE)			
	Grade 1	Grade 2	Grade 3	Grade 4
AST	> 1 – ≤ 3 x ULN	> 3 – ≤ 5 x ULN	> 5 – ≤ 20 x ULN	> 20 x ULN
Bilirubin, Total	> 1 – ≤ 1.5 x ULN	> 1.5 – ≤ 3 x ULN	> 3 – ≤ 10 x ULN	> 10 x ULN
Calcium (hyper)	> ULN – ≤ 11.5 mg/dL > ULN – ≤ 2.9 mmol/L	> 11.5 – ≤ 12.5 mg/dL > 2.9 – ≤ 3.1 mmol/L	> 12.5 – ≤ 13.5 mg/dL > 3.1 – ≤ 3.4 mmol/L	> 13.5 mg/dL > 3.4 mmol/L
Calcium (hypo)	< LLN – 8 mg/dL < LLN – 2 mmol/L	< 8 – 7 mg/dL < 2 – 1.75 mmol/L	< 7 – 6 mg/dL < 1.75 – 1.5 mmol/L	< 6 mg/dL < 1.5 mmol/L
Cholesterol, Total	> ULN – 300 mg/dL > ULN – 7.75 mmol/L	> 300 – 400 mg/dL > 7.75 – 10.34 mmol/L	> 400 – 500 mg/dL > 10.34 – 12.92 mmol/L	> 500 mg/dL > 12.92 mmol/L
Creatinine	> 1 – ≤ 1.5 x ULN	> 1.5 – ≤ 3 x ULN	> 3 – ≤ 6 x ULN	> 6 x ULN
Glucose (hyper)	> ULN – ≤ 160 mg/dL > ULN – ≤ 8.9 mmol/L	> 160 – ≤ 250 mg/dL > 8.9 – ≤ 13.9 mmol/L	> 250 – ≤ 500 mg/dL > 13.9 – ≤ 27.8 mmol/L	> 500 mg/dL > 27.8 mmol/L

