5. Subjects with DTC must be receiving thyroxine suppression therapy and levels of thyroid stimulating hormone (TSH) should not be elevated (TSH should be ≤ 5.50 mU/L). When tolerated by the subject, thyroxine dose should be changed to achieve TSH suppression (TSH < 0.50 mU/L)
6. Subjects with known central nervous system (CNS) primary tumors or metastases who have completed brain therapy (such as radiotherapy, stereotactic radiosurgery or surgical resection), and have remained clinically stable, asymptomatic and off of steroids for 2 weeks prior to Cycle 1 Day 1 will be eligible
7. Male or female subjects age 2 years to < 18 , (≤ 25 years for osteosarcoma subjects) at the time of informed consent
8. Lansky play score $\geq 50\%$ or Karnofsky Performance Status score $\geq 50\%$ ([Appendix 4](#) and [Appendix 5](#), respectively). Use Karnofsky for subjects ≥ 16 years of age and Lansky for subjects < 16 years of age
9. Life expectancy ≥ 3 months
10. Adequate bone marrow function as evidenced by:
 - a. absolute neutrophil count (ANC) $\geq 1.0 \times 10^9/\text{L}$

- b. (for Cohorts 3A and 3B leucocyte count $\geq 2 \times 10^9/L$; subjects with bone marrow involvement should have ANC $\geq 0.8 \times 10^9/L$ and leucocyte count $\geq 1 \times 10^9/L$)
- c. hemoglobin $\geq 8.0 \text{ g/dL}$ (a hemoglobin $< 8.0 \text{ g/dL}$ is acceptable if it is corrected by growth factor or transfusion before starting lenvatinib)
- d. platelet count $\geq 75 \times 10^9/L$

11. Adequate liver function as evidenced by:

- a. bilirubin ≤ 1.5 times the upper limit of normal (ULN)
- b. alkaline phosphatase, alanine aminotransferase (ALT), and aspartate aminotransferase (AST) $\leq 3 \times \text{ULN}$ (in the case of liver metastases $\leq 5 \times \text{ULN}$), unless there are bone metastases or bone primary tumor, in which case liver specific alkaline phosphatase must be separated from the total and used to assess the liver function instead of the total alkaline phosphatase

12. Adequate renal function as evidenced by:

- a. Serum creatinine based on age/gender as below. If serum creatinine is greater than maximum serum creatinine for age/gender as shown in the table below, then creatinine clearance (or radioisotope glomerular filtration rate [GFR]) must be $> 70 \text{ mL/min}/1.73 \text{ m}^2$ ([Appendix 6](#)).

Age	Maximum Serum Creatinine (mg/dL)	
	Male	Female
2 to < 6 years	0.8	0.8
6 to < 10 years	1	1
10 to < 13 years	1.2	1.2
13 to < 16 years	1.5	1.4

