- 60 mg/m² if 50 mg/m² \leq the calculated dose level on Cycle 1 Day 1 < 70 mg/m²

For subjects in expansion cohorts (2A, 2B and 3B), the actual dose level will be set to the planned dose level regardless of capped dose.

The planned dose level is used in the Full Analysis Set and Per Protocol Analysis Set, while the actual dose level (BSA-adjusted dose level) will be used for the Safety Analysis Set, PK Analysis Set, and DLT Analysis Set. Regarding summarization of mean and mean change from Baseline for laboratory, vital sign, and ECG data, if 2 or fewer subjects in each of the treatment groups have data for a given cycle, the applicable cycle(s) will not be summarized and the table will be curtailed. For example, if at Cycle 12 the 3 treatment groups have 4, 3 and 1 subjects, respectively, then Cycle 12 will be summarized for all treatment groups. If at Cycle 13, the 3 treatment groups have 2, 2 and 1 subject, respectively, and at subsequent cycles no treatment has 3 or more subjects, then the table will not be produced for Cycle 13 and all subsequent cycles. However, for shift tables and other analyses of worst postbaseline values, all data will be included.

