5.6.3.1 Hematology and Clinical Chemistry

Laboratory parameters will be reported using the following methods for hematology and clinical chemistry:

- Descriptive summary statistics for all major hematology and clinical parameters and their changes from baseline will be calculated (n, mean, SD, median, Q1, Q3, min, max)
- Shifts from Baseline to worst postbaseline visits relative to CTCAE grade (presenting each dose level and overall shift table for all clinical chemistry parameters and the following hematology parameters: hemoglobin, platelets, WBC (leukocytes), neutrophils (ANC), and lymphocytes)

All hematology and clinical chemistry laboratory parameters will be listed by subject and visit.

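### SAP 13.3 gives hemoglobin below 6.5 g/dL no laboratory grade, so the graded listing, and for some subjects the worst-grade shift table, would not show the most severe anemia

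*SAP*

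**What the plan says.** SAP 13.3 sets out the CTCAE bands for laboratory values. For hemoglobin, Grade 2 is "< 10 – 8 g/dL < 6.2 – 4.9 mmol/L", Grade 3 is "< 8 – 6.5 g/dL < 4.9 – 4 mmol/L", and Grade 4 is a dash.

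Two planned outputs use a laboratory grade:

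- SAP 5.6.3 includes the CTCAE grade in the laboratory listing.
- SAP 5.6.3.1 plans "Shifts from Baseline to worst postbaseline visits relative to CTCAE grade" and limits the hematology part to "hemoglobin, platelets, WBC (leukocytes), neutrophils (ANC), and lymphocytes".

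On completeness, SAP 5.3.6 states that "for shift tables and other analyses of worst postbaseline values, all data will be included". SAP 8.1 adds that worst-grade analyses use all observations, and that unscheduled assessments enter the shift tables. Neither section says what to do with a value that fits no band. SAP 9 leaves derivation rules to separate programming documents. Protocol Appendix 2 gives only the general CTCAE severity scale, with no hemoglobin cut-off.

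**The concern.** A grading scale should cover its severe end. Here the bands stop at 6.5 g/dL and nothing continues below, so the lowest hemoglobin values are the ones that cannot be graded. The error runs in one direction: applied literally, the table can make anemia look milder but never worse.

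Low values are foreseeable in this population. Cohorts 3A and 3B receive ifosfamide and etoposide, and Protocol 9.4.1.11 anticipates myelosuppression. Protocol 9.3.1 admits subjects at 8.0 g/dL, and a lower hemoglobin "is acceptable if it is corrected by growth factor or transfusion before starting lenvatinib". This shows that the lower end of the scale may be needed. It does not show how often.

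At stake is the accuracy of two descriptive safety outputs: the graded listing and the hemoglobin shift table. No primary endpoint depends on the row. Under Protocol 9.4.1.1, dose-limiting toxicities are determined by the investigator and the medical monitor.

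**Working it through.** **Step 1. Is the lower bound a stray figure?** The row equates 10 g/dL with 6.2 mmol/L, a ratio of 0.62. Then 6.5 × 0.62 = 4.03, against a printed bound of 4 mmol/L. The two units agree, so the floor is a stated cut-off in both. SAP 5.6.3 summarizes laboratory results in SI units, and the gap exists in either unit.

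**Step 2. Does any other row shown have the same gap?** Take a value just beyond the last printed bound of each row and grade it.

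| Row | Grade 3 ends at | Grade 4 | Grade beyond the last bound |
|---|---|---|---|
| Hemoglobin | 6.5 g/dL (4 mmol/L) | dash | none |
| Platelets | 25 × 10⁹/L | below 25 | 4 |
| Leukocytes | 1 × 10⁹/L | below 1 | 4 |
| Lymphocytes (hypo) | 0.2 × 10⁹/L | below 0.2 | 4 |
| Neutrophils | 0.5 × 10⁹/L | "< 500/mm ³ < 0.5 x 10 ⁹ /L" | 4 |
| Calcium (hypo) | 6 mg/dL | below 6 | 4 |
| Albumin | open, below 2 g/dL | blank | 3 |
| Lymphocytes (hyper) | open, "> 20,000/mm ³ > 20 x 10 ⁹ /L" | dash | 3 |

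The rows graded on high values only (for example ALT, AST, bilirubin and creatinine) have an open Grade 4. A row without Grade 4 is therefore not itself the problem: albumin and lymphocytes (hyper) also lack one, but their Grade 3 is open-ended. Only hemoglobin combines a closed Grade 3 with an empty Grade 4.

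**Step 3. Grade hemoglobin values by the printed row.**

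- 9 g/dL: Grade 2
- 7.9 g/dL: Grade 3
- 6.5 g/dL: Grade 3
- 6.4, 6.0 and 5.0 g/dL: no grade

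**Step 4. Follow this into the shift table.** Three illustrative subjects have a lowest value of 6.0 g/dL. The column for the printed row assumes that an ungraded value is passed over.

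| Postbaseline values (g/dL) | Worst grade, printed row | Grade 3 opened | Grade 4 filled as below 6.5 |
|---|---|---|---|
| 9 and 6.0 | 2 | 3 | 4 |
| all others normal, and 6.0 | no abnormal grade | 3 | 4 |
| 7.9 and 6.0 | 3 | 3 | 4 |

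The first two subjects are shown too mildly under either repair. The third already appears as Grade 3 and changes cell only if the repair is a filled Grade 4. In the graded listing, the 6.0 g/dL record lacks a grade in all three.

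**The case against.** The strongest reply is that little is lost.

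- **Subjects do not vanish.** A reader might infer that severe anemia drops out of the shift table. The SAP does not say that an unbanded value is discarded, and it says that all data are included. What follows from the table is narrower: the lowest value has no grade, and the subject is placed by the remaining values.
- **Many cells may be right already.** Protocol 9.5.1.5 requires repeat testing at least every 3 days after Grade 3 or worse hematologic toxicity until it falls below Grade 3. SAP 8.1 brings unscheduled values into the shift tables. A recovery value from 6.5 to below 8 g/dL is therefore plausible, although a transfusion could skip that range.
- **Other outputs show the event.** SAP 5.6.3.1 reports minimums and lists every hematology value, SAP 5.6.3 flags abnormal values, and SAP 5.6.2 tabulates adverse events by CTCAE v4.03 grade. Under Protocol 9.5.1.5, a laboratory abnormality that leads to intervention is an adverse event, which would capture a transfusion.
- **A rule may exist elsewhere.** The programming documents are separate, and the available text of the table stops after the glucose (hyper) row, so a later footnote cannot be excluded.

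The first three points stand and limit the consequence. The fourth is only a possibility. None gives a grade to a value below 6.5 g/dL in the row as printed, and the promise to include all data sits badly with a table that cannot place such a value.

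**Conclusion.** The concern holds as a gap in one row, with a limited effect. Any hemoglobin below 6.5 g/dL is ungraded in the listing. The shift table is wrong under either repair only for a subject with a value below 6.5 g/dL and none from 6.5 to below 8 g/dL. This rests on applying the printed table literally, with no unseen rule covering the gap.

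Two stronger readings are not supported. First, a reader might attach a count. Cohorts 3A and 3B plan 12 + 18 = 30 to 24 + 18 = 42 subjects; assuming that 5% to 15% fall below 6.5 g/dL gives 0.05 × 30 = 1.5 to 0.15 × 42 = 6.3. The documents supply no such rate, and the figure counts low values rather than changed table entries. Second, a reader might infer which edge is the mistake. The printed dash and the albumin and lymphocytes (hyper) rows favor an open Grade 3. The closed bound at 6.5 g/dL would equally fit an omitted Grade 4, as in the platelet, leukocyte and neutrophil rows. The documents do not settle it.

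**What to change.** Reconcile the hemoglobin row of SAP 13.3 with the cited CTCAE v4.03 so that every value below 8 g/dL has a grade. There are two ways:

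- Make Grade 3 open-ended (< 8 g/dL; < 4.9 mmol/L) and keep the dash. This fits the table's treatment of albumin and lymphocytes (hyper).
- Fill Grade 4, if v4.03 gives a laboratory cut-off for it.

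Then program the hemoglobin shift table and the listing grades from the corrected row. If a programming document already handles values below 6.5 g/dL, its rule should be stated in SAP 13.3. The cost is one cell in an appendix and one programming cut-off, with no new data.
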